### 1264 **8.1.2 Reportable Adverse Events**

1265 For this protocol, a reportable adverse event includes any untoward medical occurrence that  
1266 meets one of the following criteria:

- 1267 1. An SAE
- 1268 2. An ADE as defined in Section 8.1.1, unless excluded from reporting in Section 8.2
- 1269 3. An AE as defined in Section 8.1.1 occurring in association with a study procedure
- 1270 4. An AE as defined in Section 8.1.1 which leads to discontinuation of a study device for two or  
1271 more hours
- 1272 5. Hypoglycemia meeting the definition of severe hypoglycemia as defined below
- 1273 6. Diabetic ketoacidosis (DKA) as defined below or in the absence of DKA, hyperglycemia or  
1274 ketosis event meeting the criteria defined below

1275

1276 Hypoglycemia and hyperglycemia not meeting the criteria below will not be recorded as adverse  
1277 events unless associated with an Adverse Device Effect. Skin reactions from sensor adhesive  
1278 placement are only reportable if severe and/or required treatment.

1279

1280 Pregnancy occurring during the study will be reported as an AE (see Section 8.3).

1281

1282 All reportable AEs—whether volunteered by the participant, discovered by study personnel  
1283 during questioning, or detected through physical examination, laboratory test, or other means—  
1284 will be reported on an AE form online. Each AE form is reviewed by the Medical Monitor to  
1285 assess safety and to verify the coding and the reporting that is required.

1286

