1396 All UADEs and ADEs as defined in Section 8.1.1 will be reported on both a device issue form  
1397 and AE form, except for skin reactions from CGM sensor placement or pump infusion set  
1398 placement that are not severe and/or require treatment.

1399  
1400 Device complaints and device malfunctions for the investigational device will be reported except  
1401 in the following circumstances. These occurrences are expected and will not be reported on a  
1402 Device Issue Form assuming criteria for a UADE or ADE have not been met:

- 1403 • CGM sensor lasting fewer days than expected per manufacturer
- 1404 • CGM tape adherence issues
- 1405 • Pump infusion set occlusion (including tubing and cartridge) not leading to ketosis  $\geq 0.6$   
1406 mmol/L or in the absence of checking for blood ketones, blood glucose  $>350$  mg/dL  
1407 (19.4 mmol/L); and not requiring an intervention other than replacing the tubing and/or  
1408 cartridge
- 1409 • Battery lifespan deficiency due to inadequate charging or extensive wireless communication
- 1410 • Intermittent device component disconnections/communication failures not requiring  
1411 system replacement or workaround/resolution not specified in user guide/manual.
- 1412 • Device issues clearly addressed in the user guide manual that do not require additional  
1413 troubleshooting

1414  
1415 **8.3 Pregnancy Reporting**

1416 If pregnancy occurs, the participant will be discontinued from the study. The occurrence of  
1417 pregnancy will be reported on an AE Form.

1418  
1419 **8.4 Timing of Event Reporting**  
1420 SAEs possibly related to an investigational device or study participation and UADEs must be  
1421 reported to the Coordinating Center within 24 hours of the site becoming aware of the event.  
1422 This can occur via phone or email, or by completion of the online serious adverse event form and  
1423 device issue form if applicable. If the form is not initially completed, it should be completed as  
1424 soon as possible after there is sufficient information to evaluate the event. All other reportable  
1425 ADEs and other reportable AEs should be submitted by completion of the online form within  
1426 seven days of the site becoming aware of the event.

1427  
1428 The Coordinating Center will notify all participating investigators of any adverse event that is  
1429 serious, related, and unexpected. Notification will be made within 10 days after the Coordinating  

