## 1447 **8.5 Stopping Criteria**

### 1448 **8.5.1 Participant Discontinuation of Investigational Device**

1449 Rules for discontinuing investigational device use are described below.

1450

- 1451 • The investigator believes it is unsafe for the participant to continue on the intervention.  
1452 This could be due to the development of a new medical condition or worsening of an  
1453 existing condition; or participant behavior contrary to the indications for use of the device  
1454 that imposes on the participant's safety
- 1455 • The participant requests that the treatment be stopped
- 1456 • Two distinct episodes of DKA (as defined in section 8.1.2) unrelated to infusion set  
1457 failure
- 1458 • A single episode of severe hypoglycemia (as defined in section 8.1.2.1) or DKA (as  
1459 defined in section 8.1.2.2) for which use of the investigational device (AHCL system) is  
1460 considered by either the Medical Monitor or DSMB to be the cause of the event (ie, there  
1461 is not another plausible assignable cause) **in the absence of a device malfunction (e.g.,**  
1462 **software bug) for which the automated insulin delivery algorithm is temporarily or**  
1463 **permanently discontinued for all subjects**
- 1464 • Two distinct severe hypoglycemia events (as defined in Section 8.1.2.1)

1465  
1466 Even if the investigational device system is discontinued, the participant will be encouraged to  
1467 remain in the study through the final study visit. If the investigational device (ie. AHCL system)  
1468 is discontinued for safety reasons, the investigator with concurrence of the Medical Monitor can  
1469 switch the participant to either use the 670G 3.0 HCL system in closed loop (if the participant  
1470 entered the trial on 670G 3.0 HCL using closed loop) or to 670G 3.0 HCL system but in open  
1471 loop only.

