### 1472 **8.5.2 Criteria for Suspending or Stopping Overall Study**

1473 In the case of an unanticipated system malfunction of the investigational device resulting in a  
1474 severe hypoglycemia or DKA event (both defined in Section 8.1), use of the investigational  
1475 device system will be suspended while the problem is diagnosed.

1476  
1477 In addition, study activities could be similarly suspended if the manufacturer of any constituent  
1478 study device requires stoppage of device use for safety reasons (e.g. product recall). The affected  
1479 study activities may resume if the underlying problem can be corrected by a protocol or system  
1480 modification that will not invalidate the results obtained prior to suspension.

1481  
1482 The study Medical Monitor will be informed of all adverse events and adverse device events that  
1483 are reported during the study and will review compiled safety data at periodic intervals  
1484 (generally timed to the review of compiled safety data by the DSMB). The Medical Monitor may  
1485

1486 request suspension of study activities or stoppage of the study if deemed necessary based on the  
1487 totality of safety data available.

1488

1489 **8.6 Independent Safety Oversight**

1490 A Data and Safety Monitoring Board (DSMB) will review compiled safety data at periodic  
1491 intervals (typically every six months). In addition, the DSMB will review all DKA and severe  
1492 hypoglycemia events irrespective of relatedness to study device use, and all serious events  
1493 (including UADEs) related to the study device use at the time of occurrence. The DSMB also  
1494 will be informed of any ADEs not meeting criteria for a UADE if the Medical Monitor requests  
1495 the DSMB review. The DSMB can request modifications to the study protocol or suspension or  
1496 outright stoppage of the study if deemed necessary based on the totality of safety data available.  
1497 Details regarding DSMB review will be documented in a separate DSMB document.

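### The section 8.4 reporting clock does not support the review of severe hypoglycemia and DKA that protocol sections 8.5.1 and 8.6 describe

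*Protocol*

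**What the plan says.** Section 8.4 defines the fast track: "SAEs possibly related to an investigational device or study participation and UADEs must be" "reported to the Coordinating Center within 24 hours of the site becoming aware of the event". The remaining reportable "ADEs and other reportable AEs should be submitted by completion of the online form within" "seven days of the site becoming aware of the event".

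Section 8.1.2 lists what is reportable. SAEs are item 1. Item 5 is "Hypoglycemia meeting the definition of severe hypoglycemia as defined below", and DKA falls under item 6. Neither is declared an SAE. The same section says that the Medical Monitor reviews each AE form, and section 8.1.5 gives the Medical Monitor the last word on causality.

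Section 8.6 has the DSMB look at compiled safety data at "intervals (typically every six months). In addition, the DSMB will review all DKA and severe" "hypoglycemia events irrespective of relatedness to study device use, and all serious events" related to device use, UADEs included, as they occur. It leaves further detail to a separate DSMB document.

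Under section 8.5.1, AHCL use ends after a single severe hypoglycemia or DKA event for which the device is "considered by either the Medical Monitor or DSMB to be the cause of the event (ie, there" is no other plausible cause). An exception applies where a device malfunction leads to the algorithm being withdrawn for all participants.

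**The concern.** Section 8.6 removes the relatedness filter for these two events. Section 8.4 keeps that filter and adds a seriousness filter. The site's preliminary rating therefore decides whether the Medical Monitor and DSMB hear within one day or within seven, although part of their task is to check that rating. The events on which an independent opinion adds most, those the site calls non-serious or unrelated, are allowed to travel slowest.

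At stake is the speed of two safeguards: the DSMB's event-by-event review, and the causality finding on which the single-event rule depends. One site also cannot see a pattern across sites. The efficacy analyses are not affected.

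**Working it through.** The plan gives no figure to reproduce. The main check sets the sections side by side; a short calculation then sizes the workload of a change.

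**1. Must these events be SAEs?** No.
- Severe hypoglycemia (8.1.2.1) requires altered consciousness and active help from another person. Glucagon or carbohydrate given at home by a parent can meet this without admission.
- DKA (8.1.2.2) requires treatment in a health care facility. The SAE criterion (8.1.1) is inpatient hospitalization, so emergency treatment and discharge can meet the first and not the second.
- Unless an event is life-threatening or meets another fixed criterion, seriousness rests on the investigator's judgment that it is medically significant.

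**2. Will they be UADEs?** Seldom on their own account. A UADE must be serious and unanticipated, and section 1.4 lists both events as known risks.

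**3. Which clock applies?**

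| Site's rating of the event | Limit in 8.4 | Covered by DSMB event review in 8.6 |
|---|---|---|
| UADE | 24 hours | yes |
| Serious, at least possibly related | 24 hours | yes |
| Serious; unrelated, unlikely related or not assessable | 7 days | yes |
| Not serious, any causality rating | 7 days | yes |

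The last row includes a non-serious event that the site itself considers related to AHCL. That event bears directly on the single-event rule in 8.5.1, and it still has seven days.

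**4. Size of the delay.** Both clocks start at site awareness, so the extra delay is at most 7 − 1 = 6 days per event. The time from the event to site awareness comes on top and is the same under either clock.

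**5. Workload if these events move to 24 hours.** Section 1.1.4 reports no severe hypoglycemia or ketoacidosis in 12,389 patient-days of the 670G pivotal trial. With zero events, the one-sided 95% Poisson upper bound on the rate is −ln(0.05)/12,389 = 2.996/12,389 = 0.000242 per patient-day.
- Both periods in auto mode: 112 × 168 = 18,816 days; × 0.000242 = about 4.5 events.
- AHCL only: 112 × 84 = 9,408 days; × 0.000242 = about 2.3 events.

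These figures count all severe hypoglycemia and DKA, including events already on the fast track. They assume that all 112 participants complete both periods, and they leave out the run-in and the 6–10 days before auto mode. They are 95% upper limits at the pivotal-trial rate, not maxima. The trial enrolls younger people with HbA1c of 7.0–11.0%, against a mean age of 37.8 years and mean HbA1c of 7.4% in the pivotal trial, so its rate may be higher. At two or three times the bounding rate the totals would be about 9 or 14 events.

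**The case against.** A reader might infer that the single-event rule and the DSMB review cannot operate at all under 8.4. The documents do not support that. Section 8.5.1 sets no deadline, so a form arriving on day seven makes its rule late, not void. Seven days is a maximum. The first bullet of 8.5.1 lets the investigator, who knows first, stop the device immediately on safety grounds.

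The gap is also narrower than all severe hypoglycemia and DKA. Many such episodes could be rated serious as medically significant, and the possibly-related category in 8.1.3 is a low bar. A serious event with no plausible cause other than AHCL should therefore already be on the 24-hour track.

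A reader might also infer that a system fault would leave every AHCL user exposed for a week. That is not supported either. The suspension rule in 8.5.2 concerns an unanticipated malfunction, and the UADE definition extends to unanticipated serious problems associated with a device. A serious event of that kind would usually be expedited.

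On 8.6, the phrase about timing can be read as attaching only to related serious events. It can also mean event-driven rather than six-monthly review. Read literally, even 24 hours would not satisfy it. The separate DSMB document, not available here, may say more.

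These points limit the consequences but do not remove the mismatch. On either reading of the timing phrase, section 8.6 places all severe hypoglycemia and DKA outside the six-monthly cycle and without a relatedness filter. Read alongside 8.4, a DSMB document cannot speed up a report that a site is still entitled to hold. The investigator's power to stop does not replace a check meant for cases where the site sees no device cause.

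**Conclusion.** The mismatch is real and of modest size. A severe hypoglycemia or DKA event that the site rates non-serious, or serious but not possibly related, may be reported up to seven days after site awareness, six days later than on the fast track. This can delay the DSMB review in 8.6 and the causality judgment that 8.5.1 relies on; it does not disable either.

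The reading of 8.4 rests on the text alone. The conflict with DSMB timing is strongest if the timing phrase in 8.6 covers all severe hypoglycemia and DKA, which is the more natural reading but not the only one.

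A further gap for SAEs related to the 670G 3.0, which is a study device but not the investigational one, might be inferred. The wording on study participation in 8.4 largely covers it.

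**What to change.** Reconcile 8.4 with 8.6. Add to the existing 24-hour category every event that meets the protocol definition of severe hypoglycemia (8.1.2.1) or DKA (8.1.2.2), on either study device, regardless of seriousness or the site's causality rating. Keep seven days for all other reportable events. Leave the criteria in 8.5.1 and 8.5.2 unchanged; only reporting time is affected. In the same edit, state in 8.6 which events its timing phrase covers, and check the separate DSMB document for consistency.

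The cost is a sentence in each section, a matching line in the site manual, and faster paperwork for the small number of events estimated above.

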## 1447 **8.5 Stopping Criteria**

### 1448 **8.5.1 Participant Discontinuation of Investigational Device**

1449 Rules for discontinuing investigational device use are described below.

1450

- 1451 • The investigator believes it is unsafe for the participant to continue on the intervention.  
1452 This could be due to the development of a new medical condition or worsening of an  
1453 existing condition; or participant behavior contrary to the indications for use of the device  
1454 that imposes on the participant's safety
- 1455 • The participant requests that the treatment be stopped
- 1456 • Two distinct episodes of DKA (as defined in section 8.1.2) unrelated to infusion set  
1457 failure
- 1458 • A single episode of severe hypoglycemia (as defined in section 8.1.2.1) or DKA (as  
1459 defined in section 8.1.2.2) for which use of the investigational device (AHCL system) is  
1460 considered by either the Medical Monitor or DSMB to be the cause of the event (ie, there  
1461 is not another plausible assignable cause) **in the absence of a device malfunction (e.g.,**  
1462 **software bug) for which the automated insulin delivery algorithm is temporarily or**  
1463 **permanently discontinued for all subjects**
- 1464 • Two distinct severe hypoglycemia events (as defined in Section 8.1.2.1)

1465  
1466 Even if the investigational device system is discontinued, the participant will be encouraged to  
1467 remain in the study through the final study visit. If the investigational device (ie. AHCL system)  
1468 is discontinued for safety reasons, the investigator with concurrence of the Medical Monitor can  
1469 switch the participant to either use the 670G 3.0 HCL system in closed loop (if the participant  
1470 entered the trial on 670G 3.0 HCL using closed loop) or to 670G 3.0 HCL system but in open  
1471 loop only.

### 1472 **8.5.2 Criteria for Suspending or Stopping Overall Study**

1473 In the case of an unanticipated system malfunction of the investigational device resulting in a  
1474 severe hypoglycemia or DKA event (both defined in Section 8.1), use of the investigational  
1475 device system will be suspended while the problem is diagnosed.

1476  
1477 In addition, study activities could be similarly suspended if the manufacturer of any constituent  
1478 study device requires stoppage of device use for safety reasons (e.g. product recall). The affected  
1479 study activities may resume if the underlying problem can be corrected by a protocol or system  
1480 modification that will not invalidate the results obtained prior to suspension.

1481  
1482 The study Medical Monitor will be informed of all adverse events and adverse device events that  
1483 are reported during the study and will review compiled safety data at periodic intervals  
1484 (generally timed to the review of compiled safety data by the DSMB). The Medical Monitor may  
1485

1486 request suspension of study activities or stoppage of the study if deemed necessary based on the  
1487 totality of safety data available.

1488

1489 **8.6 Independent Safety Oversight**

1490 A Data and Safety Monitoring Board (DSMB) will review compiled safety data at periodic  
1491 intervals (typically every six months). In addition, the DSMB will review all DKA and severe  
1492 hypoglycemia events irrespective of relatedness to study device use, and all serious events  
1493 (including UADEs) related to the study device use at the time of occurrence. The DSMB also  
1494 will be informed of any ADEs not meeting criteria for a UADE if the Medical Monitor requests  
1495 the DSMB review. The DSMB can request modifications to the study protocol or suspension or  
1496 outright stoppage of the study if deemed necessary based on the totality of safety data available.  
1497 Details regarding DSMB review will be documented in a separate DSMB document.

## 1498 Chapter 9: Miscellaneous Considerations

1499

### 1500 9.1 Drugs Used as Part of the Protocol

1501 U-100 rapid acting insulin analogues, Aspart or Lispro, will be used during the study since these  
1502 are the only insulins approved for the study pumps.

1503

### 1504 9.2 Collection of Medical Conditions and Medications

1505 Pre-Existing Condition: Any medical condition that is either present at screening, a chronic  
1506 disease, or a prior condition that could impact the participant's health during the course of the  
1507 study (e.g., prior myocardial infarction or stroke).

1508 Medical Conditions during the study: In addition to conditions meeting the reporting  
1509 requirements for an adverse event or device issues as described in Section 8.1 and Section 8.2,  
1510 the following medical conditions should also be reported: (1) new diagnosis of a chronic disease  
1511 (not present at the time of enrollment); and (2) any medical condition that could affect the  
1512 participant's ability to carry out any aspect of the protocol or could affect an outcome  
1513 assessment.

1514 Medications: All medication for the treatment of chronic pre-existing conditions, medical  
1515 conditions, and/or adverse events that the participant is currently taking at screening and during  
1516 the course of the study should be recorded. Nutraceuticals and preventative treatment also should  
1517 be recorded.

### 1518 9.3 Prohibited Medications, Treatments, and Procedures

1519 Acetaminophen/Paracetamol may cause unreliable glucose sensor readings. If possible,  
1520 participants should avoid taking medications with acetaminophen while in Auto Mode. If  
1521 acetaminophen is taken, participants will be instructed to turn off auto mode and use BG meter  
1522 readings to follow glucose levels. Additional BG meter readings should not be used to calibrate  
1523 the sensor. Auto mode should be restarted when BG meter and CGM readings are consistently in  
1524 close agreement which may take up to 8-12 hours.

1525

1526 Exclusionary medications are:

- 1527 • Oral or parenteral glucocorticoids taken within 1 month prior to enrollment, or plans to take  
1528 oral or parenteral glucocorticoids within the planned study duration. Exceptions: Short term  
1529 oral or parenteral glucocorticoids up to 7 days
- 1530 • Any antidiabetic agents other than insulin

1531

### 1532 9.4 Participant Compensation

1533 Participant compensation will be specified in the informed consent form.

1534

### 1535 9.5 Participant Withdrawal

1536 Participation in the study is voluntary, and a participant may withdraw at any time. For  
1537 participants who withdraw, their data will be used up until the time of withdrawal. An early  
1538 termination visit may be completed to collect final study data.

1539

1540 If participants wish to discontinue using the study device without withdrawing, participants will  
1541 be encouraged to remain in the study through the final study visit.

1542

1543 **9.6 Confidentiality**

1544 For security and confidentiality purposes, participants will be assigned an identifier that will be  
1545 used instead of their name. Protected health information gathered for this study will be shared  
1546 with the coordinating center, the Jaeb Center for Health Research in Tampa, FL. De-identified  
1547 participant information may also be provided to research sites involved in the study.

## 1548 Chapter 10: Statistical Considerations

1549

### 1550 10.1 Statistical and Analytical Plans

1551 The approach to sample size and statistical analyses are summarized below. A detailed statistical  
1552 analysis plan will be written and finalized prior to the completion of the study. The analysis plan  
1553 synopsis in this chapter contains the framework of the anticipated final analysis plan.

1554

### 1555 10.2 Statistical Hypotheses

1556 The co-primary outcomes are CGM-measured metrics over 12-week periods (excluding time  
1557 before auto mode is turned on):

- 1558 • Superiority in percent time  $>180$  mg/dL (10.0 mmol/L) from 6AM to 11:59PM
- 1559 • Non-inferiority in CGM-measured time  $<54$  mg/dL (3.0 mmol/L) calculated over the full 24  
1560 hours of the day

1561

1562 The study hypotheses can be stated as follows:

1563

